6.1.2. Dose-limiting Toxicity

Dose-limiting toxicity (DLT) will be assessed during the first cycle (including the PK lead-in period for patients in Part A1). The occurrence of any toxicity outlined in [Table 7](#) that is clinically significant will be considered a DLT, excluding toxicities clearly related to disease progression or intercurrent illness. The investigator must report all DLTs to the Sponsor promptly during the dose escalation part and well in advance of the dose escalation call. In addition, meetings between the Sponsor and investigators will be held on a regular basis to review safety data and in the event of emerging safety issues.

Table 7: Definition of Dose Limiting Toxicity

Toxicity	DLT Definition
Hematologic	
 • Grade 4 neutropenia lasting >7 consecutive days • Grade 4 thrombocytopenia • Grade 3 thrombocytopenia associated with clinically significant bleeding requiring intervention • Febrile neutropenia (ANC <1000/mm³ with a single body temperature of >38.3°C [101 °F] or a sustained temperature of ≥38°C [100.4°F] for more than 1 hour)
Hepatic	
 • Grade ≥3 total bilirubin elevation • Grade ≥3 AST and/or ALT elevation • For patients with liver metastases, AST or ALT >8 × ULN regardless of duration or AST or ALT >5 × ULN but ≤8 × ULN lasting ≥7 consecutive days
	
 • Hy's Law criteria concurrent observation of the following, with no other reason found to explain the findings (such as viral hepatitis A, B, or C; pre-existing or acute liver disease; or another drug capable of causing the observed liver injury): 
 – Elevated aminotransferase enzymes >3 × ULN – Associated with an increase in bilirubin >2 × ULN – Absence of initial findings of cholestasis (elevated ALP)
Renal	
 • Calculated CrCl <30 mL/min for >3 days despite optimal supportive care
Skin	
 • Grade ≥3 skin toxicity uncontrolled by adequate skin therapy, including topical steroid and/or systemic corticosteroid therapy that does not return to Grade ≤2 within 7 days
Other Nonhematologic	
 • Any other Grade ≥3 toxicities with the following exceptions: 
 – Grade 3 nausea, vomiting, and diarrhea lasting <72 hours despite optimal supportive care. Grade 4 vomiting or diarrhea will be considered a DLT. – Fatigue lasting <7 days – Asymptomatic Grade 3 electrolyte abnormality with a duration of ≤72 hours that can be substituted or treated and are clinically uncomplicated (eg, not requiring hospitalization). – Grade 3 amylase or lipase elevation not associated with symptoms or clinical manifestations of pancreatitis

Toxicity	DLT Definition
Other	
 • Prolonged dose interruption (>2 weeks) in initiating Cycle 2 due to study drug-related toxicity) • Any study drug related AE(s) leading to treatment discontinuation during Cycle 1 despite optimal supportive treatment • Any death not clearly due to the underlying disease or extraneous causes. • Any other toxicity deemed a DLT and agreed upon between Sponsor and Investigator

Abbreviations: AE=adverse event; ALP=alkaline phosphatase; ALT=alanine aminotransferase; ANC=absolute neutrophil count; AST=aspartate aminotransferase; DLT=dose-limiting toxicity; ULN=upper limit of normal

A patient evaluable for DLT is defined as a patient who either experienced a DLT during the first cycle (including the PK Lead-in period for patients in Part A1), or who completed the first cycle without experiencing a DLT and with at least 80% of study treatment administered. Patients who are not evaluable for DLTs may be replaced. Trends for toxicities observed after the DLT period will be considered when selecting the RP2D.

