Grade 1 and 2	No dose modifications required Topical steroid (eg, hydrocortisone 2.5%) and clindamycin cream BID, as needed, and consider oral antibiotic (eg, doxycycline 100 mg BID) for 2 to 4 weeks
Grade ≥ 3	Suspend dose until resolved to \leq Grade 2 and manage as shown above for Grade 1/2 considering additional oral steroids, then: 
 • If resolved ≤ 14 days, resume at the same dose level and consider prophylactic management of skin rash • If resolved > 14 days or re-occurrence, resume at next lower dose level
QT prolongation	
Grade 1	
 • Repeat ECG (triplicates, 2-3 minutes apart) • If QTcF is still on average > 450 ms, check electrolytes and replace to maintain $K \geq 4.0$ mmol/L, $Mg \geq 1.8$ mg/dL (0.9 mmol/L) and $Ca > 8.0$ mg/dL (2.0 mmol/L) and repeat ECG • No dose modifications required
Grade 2	
For first occurrence:
 
 • Repeat ECG (triplicates, 2-3 minutes apart) • Check electrolytes and replace to maintain $K \geq 4.0$ mmol/L, $Mg \geq 1.8$ mg/dL (0.9 mmol/L) and $Ca > 8.0$ mg/dL (2.0 mmol/L) and repeat ECG • If QTcF is still on average > 481 ms, suspend drug until resolved to \leq Grade 1, and then resume at the same dose level 
If re-occurrence:
 
 - Suspend drug until resolved to \leq Grade 1 and then resume at the next lower dose level
Grade 3	
 • Repeat ECG (triplicates, 2-3 minutes apart) • Check electrolytes and replace to maintain $K \geq 4.0$ mmol/L, $Mg \geq 1.8$ mg/dL (0.9 mmol/L) and $Ca > 8.0$ mg/dL (2.0 mmol/L) and repeat ECG • If QTcF is still > 500 ms and/or > 60 ms change from baseline, suspend drug until resolved to \leqGrade 1 and obtain an evaluation by a cardiologist. If study drug can be resumed, it should be at the next lower dose level • If re-occurrence, consider discontinuing the study drug
Grade 4	Discontinue study drug

Grade by CTCAE v5.0	Management Recommendation
Interstitial Lung Disease (ILD) / Pneumonitis (see also Section 6.4.4.3)	
Grade 1	No dose modifications required, consider follow-up at regular intervals as per institutional standards
Grade 2	Suspend dose until resolved to \leq Grade 1, then: 
 • If resolved \leq14 days, maintain dose level • If resolved $>$14 days, resume at the next lower dose level If clinical symptoms persist/worsen despite treatment, consider discontinuing study drug

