Grade 3 and 4	Discontinue study drug
Corneal ulceration	
Grade \geq 3	Discontinue study drug
Other Non-hematologic Toxicities	
Grade 1 and Grade 2	No dose modifications required, administer supportive therapy as indicated
Grade 3	Suspend dose until resolved to \leq Grade 1 or baseline (\leq Grade 2 for toxicities that are manageable by supportive therapy, such as asymptomatic electrolyte changes, dyspepsia, hypertension), then: 
 • If resolved \leq14 days, resume at the same dose level • If resolved $>$14 days or re-occurrence, resume at next lower dose level
Grade 4	Suspend dose until resolved to \leq Grade 1 or baseline, then resume at next lower dose level. Discontinue study drug if re-occurrence or occurrence of an irreversible treatment related clinically significant event.

Abbreviations: ALP=alkaline phosphatase; ALT=alanine aminotransferase; AST=aspartate aminotransferase; BID=twice daily; CTCAE=Common Terminology Criteria for Adverse Events; ECG=electrocardiogram; QD=once daily; QTc=corrected QT interval; QTcF=Fridericia's Correction Formula for corrected QT interval; T-bil=total bilirubin; ULN=upper limit of normal.

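### Drug-related toxicity that meets no specific Table 7 line but takes a patient below 80% of Cycle 1 dosing enters the BOIN count only by case-by-case agreement; Grade 3-4 anemia has no DLT line

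*Protocol*

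**What the plan says.** **Who is counted.** Protocol 6.1.2 sets the window: "Dose-limiting toxicity (DLT) will be assessed during the first cycle", plus the PK lead-in for Part A1. A patient is evaluable after a DLT, or if he or she "completed the first cycle without experiencing a DLT and with at least 80% of study treatment administered". It adds: "Patients who are not evaluable for DLTs may be replaced". Protocol Table 17 (12.5) and SAP Table 3 (4.2) use essentially the same definition. None of them asks why doses were missed.

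**What is a DLT.** The hematologic row of Table 7 covers neutropenia, thrombocytopenia and febrile neutropenia. The line for any other Grade 3 or higher toxicity sits in the Other Nonhematologic row and has exceptions, one of them without a time limit: "Grade 3 amylase or lipase elevation not associated with symptoms or clinical manifestations of pancreatitis". The Other row includes "Prolonged dose interruption (>2 weeks) in initiating Cycle 2 due to study drug-related toxicity", drug-related AEs that end treatment in Cycle 1, and a catch-all: "Any other toxicity deemed a DLT and agreed upon between Sponsor and Investigator".

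**When drug is held.** Table 9 suspends TAS3351 for Grade 3 and Grade 4 anemia, and 2.2.1.5 names anemia as an anticipated risk. Table 10 suspends for Grade 3 or higher rash until it is Grade 2 or lower, "and manage as shown above for Grade 1/2 considering additional oral steroids". For other Grade 3 non-hematologic events it suspends until Grade 1 or baseline, with Grade 2 accepted "for toxicities that are manageable by supportive therapy, such as asymptomatic electrolyte changes, dyspepsia, hypertension". Section 6.2.1 keeps the 21-day cycle running through an interruption; only the start of Cycle 1 after a lead-in may be delayed.

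**What the count decides.** Section 12.7.4.1 bases escalation on the cumulative DLT rate at the current dose. Section 4.2.1 uses the same rate to call a dose safe for backfill.

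**The concern.** The evaluability rule, the DLT list and the dose-hold tables do not fit together. A site can follow Tables 9-10, hold drug for a related toxicity that Table 7 does not list, and so take the patient below 80%. That patient is then neither a DLT nor evaluable, and a replacement may be enrolled. The toxicity is missing from the Table 6 count unless someone invokes the catch-all.

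Anemia is a separate omission and works differently. A patient with Grade 4 anemia who still takes 80% of doses is scored as having no DLT. One who falls below 80% is not scored at all.

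At stake is whether, in a first-in-human escalation, the count can indicate escalation and clear a dose for backfill while omitting drug-related toxicity serious enough to interrupt Cycle 1.

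**Working it through.** **1. The plan's own boundaries.** Inputs from 12.7.4.1: φ = 0.30, φ1 = 0.6 × 0.30 = 0.18, φ2 = 1.4 × 0.30 = 0.42.

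- λ1 = ln[(1−φ1)/(1−φ)] / ln[φ(1−φ1)/(φ1(1−φ))] = ln(0.82/0.70) / ln(0.246/0.126) = 0.2365
- λ2 = ln[(1−φ)/(1−φ2)] / ln[φ2(1−φ)/(φ(1−φ2))] = ln(0.70/0.58) / ln(0.294/0.174) = 0.3585

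These match the stated 0.236 and 0.359. Escalation at floor(nλ1) and de-escalation at ceil(nλ2) reproduce all 15 entries in each row of Table 6. The elimination row (13 entries) also reproduces, assuming a uniform prior. The boundaries are sound; the question is what is fed into them.

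**2. Where 80% falls.**

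- QD: 17/21 = 81.0% passes, 16/21 = 76.2% fails.
- QD with the lead-in dose: 18/22 = 81.8% passes, 17/22 = 77.3% fails.
- BID: 34/42 = 81.0% passes, 33/42 = 78.6% fails.

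Five missed QD doses, or nine missed BID doses, remove a patient. If the 80% is read as cumulative dose, nine days at half dose (350 to 175 mg in Table 8) also do: (21 − 4.5)/21 = 78.6%. The interruption line needs more than 14 days.

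**3. Holds in Tables 9-10 set against Table 7.**

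- Suspended but not listed as a DLT: Grade 3-4 anemia; Grade 3 neutropenia beyond 3 days; Grade 4 neutropenia up to 7 days; Grade 3 thrombocytopenia without bleeding; Grade 2 ILD; Grade 2 QT prolongation confirmed on repeat.
- Suspended but tolerated by Table 7: Grade 3 rash settling within 7 days; Grade 3 fatigue under 7 days; asymptomatic Grade 3 amylase or lipase elevation.

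**4. Table 6 decisions, supposing the catch-all is not used.**

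| Patients | Evaluable only | Holds counted |
|---|---|---|
| 5 treated, 2 holds, no DLT | 0/3 escalate | 2/5 de-escalate |
| Same, both replaced by patients without a DLT | 0/5 escalate | 2/7 stay |
| 8 treated, 1 DLT, 2 holds | 1/6 escalate | 3/8 de-escalate |
| 4 treated, 1 hold, no DLT | 0/3 escalate | 1/4 stay |

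The hold proportions here are 25% to 40% (2/8 and 1/4 up to 2/5). The table shows how decisions can change, not how often.

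**5. Illustration with assumed rates.** Let p be the rate of listed DLTs and q the rate of uncounted drug-related shortfalls, as separate patients. As written, BOIN sees p/(1−q). If the shortfalls are counted, it sees p+q. At n = 6 escalation needs at most 1 DLT, so P(escalate) = P(X ≤ 1).

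| p | q | Rate as written | Rate counted | P(escalate) as written | P(escalate) counted | Fall |
|---|---|---|---|---|---|---|
| 0.15 | 0.02 | 0.153 | 0.17 | 0.769 | 0.729 | 0.04 |
| 0.15 | 0.05 | 0.158 | 0.20 | 0.758 | 0.655 | 0.10 |
| 0.15 | 0.10 | 0.167 | 0.25 | 0.737 | 0.534 | 0.20 |

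At q = 0.05 the pairs for p = 0.10, 0.20 and 0.25 are 0.875 and 0.776, 0.630 and 0.534, and 0.503 and 0.420. The fall is therefore 0.08 to 0.10 across p = 0.10 to 0.25. Keeping these patients evaluable without counting the event gives rate 0.15 and P(escalate) 0.776, slightly higher than as written.

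**The case against.** The strongest reply is that Table 7 already catches most of what matters. Drug-related discontinuation in Cycle 1 is a DLT, as are Grade 3 or higher hepatic events and most other Grade 3 or higher non-hematologic events. Those patients are evaluable and counted whatever dose they received. This stands, and it confines the point to patients who stay on drug, miss at least 5 of 21 doses and meet no specific line.

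Second, several of the events in step 3 are tolerated deliberately: Grade 4 neutropenia up to 7 days, short fatigue, rash that settles, asymptomatic enzyme elevation. Counting them would change the sponsor's definition of toxicity rather than correct an error. This also stands, and the fix respects it. It does not explain the absence of anemia.

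Third, there are safeguards. The catch-all is itself a DLT criterion. Sections 4.2.1 and 6.1.1 allow lower increments or intermediate doses for clinically relevant toxicity without requiring a DLT. Replacement is optional, safety meetings are regular, and RP2D selection uses the totality of data. SAP 5.6.1.2 and 5.6.2.3 report interruptions and their reasons, and SAP 5.3.1 tabulates evaluable patients by dose. These make the holds visible and can slow escalation. Apart from the catch-all, none changes the Table 6 count, and the catch-all is not a prespecified rule.

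A reader might infer that dropping these patients lowers the DLT rate. It does not: exclusion alone raises the listed-DLT rate slightly (0.15 becomes 0.158 at q = 0.05). What is lost is the toxicity event.

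**Conclusion.** The gap in wording is clear and worth fixing. A drug-related shortfall below 80% that meets no specific Table 7 line leaves the BOIN count unless it is adjudicated in. Grade 3-4 anemia has no line. The interruption line conflicts with 6.2.1. Read broadly, that line might catch a hold running well into Cycle 2, so it is not certain to be void, but no reading reaches a hold of 5 to 14 days.

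The size of the effect is unknown, because the documents give no interruption rate. The falls of 0.04, 0.10 and 0.20 rest on an assumed 15% listed-DLT rate, assumed hold rates of 2%, 5% and 10%, n = 6, and the catch-all never being used. At 2% the effect is small.

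A reader might go further and infer that the design would escalate through doses patients cannot tolerate, or that every toxicity-driven dose shortfall escapes the count. The documents do not support either. Patients who stop for drug-related toxicity in Cycle 1 are counted, as is most severe non-hematologic toxicity, and smaller dose increments are available without any DLT.

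**What to change.** 1. Add an anemia line to the hematologic row of Table 7, at least for Grade 4.
2. Reword the interruption line as drug-related toxicity starting in Cycle 1 that keeps TAS3351 on hold for more than 14 consecutive days, including days in Cycle 2. State in 6.1.2 that DLT status stays open until the hold ends or passes 14 days.
3. Add a DLT line for study-drug-related toxicity that prevents at least 80% of planned Cycle 1 dosing, where the hold or reduction is recommended by Tables 9-10 or judged clinically significant. Brief discretionary holds, which 6.2 permits, then do not count automatically. Keep the existing Table 7 exemptions unless the sponsor chooses otherwise, and say whether the duration limits for neutropenia and skin are among them.

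Leave the evaluability rule unchanged for all other shortfalls. A patient who meets the new line has a DLT and is already evaluable. Making other shortfalls evaluable without counting them would lower the observed rate.

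**Cost.** Wording only, with no added procedures. Escalation would be somewhat slower at doses that cause holds, and item 2 can delay a decision while a hold is open. The new lines would automatically count toward the 30% stop in 4.2.4, which is first exceeded at 4 of 10 or 7 of 20. The BOIN boundaries need no change, but the sponsor should confirm the 0.30 target for the wider definition. One limit remains: a 7-day hold from Day 8 falls below 80%, while the same hold from Day 18 misses only 4 Cycle 1 doses and does not.

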6.2. Dose and Schedule Modifications

The following general dose modification guidelines for patients receiving TAS3351 should be followed:

- Supportive treatment for any AE should be optimized before any modification is considered.
- If the symptoms of AE promptly resolve with supportive care, consideration should be given to continuing study drug along with appropriate continuing supportive care.

Recommended dose modifications are based on the occurrence of treatment-related AEs and are provided for hematological toxicities (Section 6.2.1.1) and non-hematological toxicities (Section 6.2.1.2). If an Investigator suspends treatment or reduces doses without one of the dose reduction, interruption and resumption criteria being met, this is acceptable and would not be considered a protocol deviation.

6.2.1. Dose Reduction, Interruption, and Resumption

Dose reductions for TAS3351 should be made according to [Table 8](#). No more than 3 dose reductions are allowed. If dose reductions fail to result in achieving the minimum criteria to resume treatment or if toxicities occur that would necessitate reducing TAS3351 dosing below 25 mg QD (or BID), the patient should be discontinued from TAS3351 treatment.

Table 8: Dose Reduction

TAS3351 Total Daily Dose	
Current Dose (mg/d) ^a	Reduce to (mg/d) ^a
50	25
100	50
200	100
350	175
500	300
700	500

^a In case of BID dosing, total daily dose to be divided in two equal doses to be administered 12 h apart. For a current dose of 50 mg, dose would be reduced to 25 mg QD.

Abbreviations: BID=twice daily; d=day; h=hour; mg=milligram

Patients with dose reduction of TAS3351 may be re-escalated up to the starting dose, if the toxicity leading to dose reduction has been resolved and the benefit/risk assessment favors re-escalation of TAS3351. A discussion between Investigator and the Sponsor's medical monitor is required prior to the TAS3351 dose re-escalation.

If dosing of TAS3351 needs to be interrupted, the 21-day cycle will be maintained. There will be no delay in the start of a new cycle except the start of Cycle 1 for patients with a PK Lead-in period in Part A1, if clinically indicated.

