6. STUDY TREATMENT

6.1. Study Drug Administration

TAS3351 will be administered orally once daily (QD) on Days 1 to 21 of a 21-day cycle. Patients enrolled in Part A1 will also be administered a single dose of TAS3351 on Cycle 1 Day -3 during the PK Lead-in Period. If PK, pharmacodynamic, and/or safety data indicate, twice daily (BID) dosing of TAS3351 may also be explored.

- TAS3351 should be taken at approximately the same time every day on an empty stomach and should be taken with water. Patients should not consume food 2 hours before and ending 1 hour after taking TAS3351 but will be allowed to drink water during this period. Patients should be instructed to swallow the tablets whole and not to chew or crush them.
- In the event of a dosing delay up to 12 hours (6 hours for BID dosing) after the scheduled dosing time, the patient should still take that day's dose. If the dosing delay is >12 hours (6 hours for BID dosing) or if the patient vomits after a dose, the patient should skip that dose and continue with the planned subsequent dose (skipped or missed doses should not be made up).

On PK sampling days, TAS3351 should be administered on-site after the pre-dose PK sample collection (Table 13). Actual dosing time will be recorded.

Patients will receive TAS3351 until disease progression, unacceptable toxicity, or any other discontinuation criterion or withdrawal criterion is met (Section 5.4, Section 5.6).

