6.1.1. Dose Escalation

The starting dose of TAS3351 will be 50 mg QD (Table 5). The study is designed to escalate TAS3351 up to a dose of 700 mg daily based on safety and tolerability observed, with lower increments considered, if clinically relevant toxicities are observed. The upper end of 700 mg TAS3351 total daily dose levels are based on more conservative assumptions for PK predictions and non-clinical efficacy data observed. In case of toxicity, other dose levels, such as intermediate or dose levels lower than Dose Level 1, may be explored following discussion and agreement between the Sponsor and the Investigators.

Table 5: TAS3351 Dose Levels

Dose Level	Total Daily Dose (mg/d)	Absolute and % Change from Previous Total Daily Dose
-1	25	-25 mg / -50%
1 (Starting dose)	50	-
2	100	50 mg / 100%
3	200	100 mg / 100%
4	350	150 mg / 75%
5	500	150 mg / 43%
6	700	200 mg / 40%

Note: If no DLTs observed at 700 mg QD, any further dose escalation will not exceed 33% increments.

In addition, if PK, pharmacodynamic, and/or safety data indicate that splitting the dose of TAS3351 in two daily doses might be preferable (eg, due to short half-life, saturation of exposure), then twice daily (BID) dosing of TAS3351 may be explored following discussion and agreement between the Investigators and the Sponsor. In such case, the dose of the highest QD dose shown previously to be safe and tolerable will be divided into two equal doses to be taken in the morning and evening approximately 12 hours apart. Dose escalation for twice daily dosing will follow total daily doses shown in Table 5 (ie, total daily dose divided by 2 for BID dosing).

The planned dose escalation will follow a BOIN design, [REDACTED]. For further information about statistical considerations, please see Section 12.

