6.2.1.1. Dose Modifications for Hematological Toxicities

Recommendations for dose modification due to study drug-related hematologic toxicities are presented in [Table 9](#).

Table 9: Recommendations for Management of Hematologic Toxicities

Grade by CTCAE v5.0	Management Recommendation
Grade 1 and 2	No dose modifications required
Anemia and Thrombocytopenia	
Grade 3	Suspend TAS3351 until resolved to Grade ≤ 2 or baseline, then: 
 • If resolved ≤ 14 days, resume at the same dose level • If resolved > 14 days or re-occurrence, resume at next lower dose level
Grade 4	Suspend until resolved to Grade ≤ 2 or baseline, then resume at next lower dose level
Neutropenia (ANC)	
Grade 3 lasting ≤ 3 days	No dose modifications required
Grade 3 lasting > 3 days or Grade 4	Suspend TAS3351 until resolved to Grade ≤ 2 or baseline, then 
 • If resolved ≤ 7 days, resume at the same dose level • If resolved > 7 days or re-occurrence, resume at next lower dose level
Febrile neutropenia	Suspend TAS3351 until resolved, then resume at next lower dose level

Abbreviations: ANC=absolute neutrophil count; CTCAE=Common Toxicity Criteria for Adverse Events

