6.7.1. Description of Study Drug

A description of the study drug and the recommended storage condition are provided in [Table 11](#).

Table 11: Description of TAS3351

Generic name	Not assigned
Dosage form	25, 100, and 200 mg tablets
Appearance	Pale yellow to grey solid
Formulation	TAS3351 tablets (25, 100, and 200 mg) contain 25, 100, and 200 mg of TAS3351 drug substance free base, respectively. In addition, these tablets contain the following inactive ingredients: Microcrystalline cellulose Lactose monohydrate Croscarmellose sodium Hydroxypropyl methyl cellulose Colloidal silicone dioxide Sodium stearyl fumarate Magnesium stearate HPCM-based color coating
Storage condition	Store TAS3351 tablets according to the label.

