5.6.2.2. Adverse Events

An AE is any untoward medical condition that occurs in patients while participating in this clinical trial. AEs will be coded according to the MedDRA (Version 25.1 or later) terminology, and the severity of the toxicities will be graded according to NCI CTCAE Version 5.0. Unique instances of all AEs (that is, after duplicates have been eliminated and overlapping and contiguous occurrences of the same event (same PT) have been collapsed) will be summarized.

A treatment-emergent AE (TEAE) is defined as an AE that is starting or worsening at the time of or after the first dose of study drug administration and within 30 days after the last dose of study drug and does not necessarily have a causal relationship to the use of the study drug.

The following summary tables will be generated:

- As an overall summary, summary of TEAEs with the number and percentage of patients reporting TEAEs, Grade ≥ 3 TEAEs, Treatment related AEs (TRAEs), Grade ≥ 3 TRAEs, serious adverse events (SAEs), treatment related SAEs, TEAEs leading to study drug discontinuation, dose interruption and dose reduction, and TEAEs with outcome of death.
- Summary of TEAEs (50mg cohort, 100mg cohort, 200mg cohort, 300mg cohort, 500mg cohort, any grade, Grade ≥ 3) presented by SOC and PT.

- Summary of TRAEs (50mg cohort, 100mg cohort, 200mg cohort, 300mg cohort, 500mg cohort, any grade, Grade ≥ 3) presented by SOC and PT.
- Summary of TEAEs (any grade, Grade ≥ 3) presented by dosing cohort and descending frequency of PTs (sorted by any grade PTs)
- Summary of TRAEs (any grade, Grade ≥ 3) presented by dosing cohort and descending frequency of PTs (sorted by any grade PTs)

A by-patient listing of all reported AEs will be provided for all treated Patients population, and non-TEAE will also be provided by listing separately.

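### Table 8 states no further reduction from 175 or 300 mg/d, and under optional BID dosing its equal-halves rule turns 175 mg/d into a dose the tablets cannot make

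*Protocol*

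**What the plan says.** Protocol Section 6.2.1 directs that reductions be made according to Table 8 and adds: "No more than 3 dose reductions are allowed". A patient who would need less than 25 mg QD (or BID), or who does not recover enough to resume after reductions, is to stop treatment.

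Table 8 gives one step for each of six current total daily doses: 50 to 25, 100 to 50, 200 to 100, 350 to 175, 500 to 300 and 700 to 500 mg/d. Footnote a adds: "In case of BID dosing, total daily dose to be divided in two equal doses to be administered 12 h apart". Its only exception is a current dose of 50 mg, which goes to 25 mg QD.

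Tables 9 and 10 (Sections 6.2.1.1 and 6.2.1.2) say when to reduce but not to what dose. For febrile neutropenia, for example: "Suspend TAS3351 until resolved, then resume at next lower dose level".

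BID is optional. Section 6.1.1 says "twice daily (BID) dosing of TAS3351 may be explored following discussion and agreement between the Investigators and the Sponsor", and if it is used, "Dose escalation for twice daily dosing will follow total daily doses shown in Table 5". Table 5 includes 350 mg/d. On supply, Section 6.7.1 says "TAS3351 tablets (25, 100, and 200 mg) contain 25, 100, and 200 mg of TAS3351 drug substance free base, respectively", and Section 6.1 says "Patients should be instructed to swallow the tablets whole and not to chew or crush them".

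**The concern.** Two of the doses that Table 8 assigns, 175 and 300 mg/d, do not appear in it as starting points. A patient who has been reduced to either one, recovers, and then has a recurrence is told by Table 9 or 10 to go one level lower, but the governing table names no level. The discontinuation rule does not cover this patient, who has met the resumption criteria and is far above 25 mg.

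The plan expects repeat reductions. Tables 9 and 10 call for a lower dose on recurrence of several toxicities, and SAP Section 5.6.1.2 tabulates patients with one, two and more than two reductions. One site might borrow the next Table 5 level, another might ask the sponsor, and another might stop the drug.

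The second problem is narrower: under BID, the instruction for a patient on 350 mg/d leads to a dose the pharmacy cannot dispense.

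**Working it through.** **Inputs.** The six Table 8 steps, the cap of 3 and the 25 mg floor (Section 6.2.1); two equal doses under BID (Table 8, footnote a); tablets of 25, 100 and 200 mg (Section 6.7.1), swallowed whole (Section 6.1).

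**Step 1: follow Table 8 from each planned dose, for at most three reductions.**

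| Starting dose (mg/d) | Steps stated in Table 8 | Number | Where it ends |
|---|---|---|---|
| 50 | 50, 25 | 1 | at the floor |
| 100 | 100, 50, 25 | 2 | at the floor |
| 200 | 200, 100, 50, 25 | 3 | at the cap and the floor |
| 350 | 350, 175 | 1 | no row for 175 |
| 500 | 500, 300 | 1 | no row for 300 |
| 700 | 700, 500, 300 | 2 | no row for 300 |

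The assigned doses without a row of their own are 25, 175 and 300. The discontinuation rule covers 25; nothing covers 175 or 300. Three of six planned levels therefore run out of stated steps before the cap and above the floor.

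**Step 2: can each dose be made?** All tablet strengths are multiples of 25 mg, and a 25 mg tablet exists, so a dose can be made from whole tablets exactly when it is a positive multiple of 25 mg.

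- 175 mg QD = 100 + 3 × 25: can be made.
- 175 mg/d in two equal doses: 175 / 2 = 87.5 mg = 3.5 × 25 mg: cannot be made.
- The other BID halves for Table 8 doses are 25 (from 50), 50 (100), 100 (200), 150 (300), 175 (350), 250 (500) and 350 mg (700): all can be made.
- 25 mg/d has a half of 12.5 mg, but footnote a already makes it QD.

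So 175 mg/d is the only unresolved BID failure.

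**Step 3: check the repair.** Add 175 to 100 and 300 to 200. Each cut is (old − new) / old.

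- From 350 QD: 350, 175, 100, 50; cuts 50.0%, 42.9%, 50.0%.
- From 500: 500, 300, 200, 100; cuts 40.0%, 33.3%, 50.0%.
- From 700: 700, 500, 300, 200; cuts 28.6%, 40.0%, 33.3%.
- From 350 BID, with 150 in place of 175: 350, 150, 100, 50; cuts (350 − 150) / 350 = 57.1%, 33.3%, 50.0%; halves 175, 75, 50 and 25 mg.

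Every level from 200 mg/d upward then has three stated steps. Every QD dose is a multiple of 25 mg, as is every BID half on the chains from 350, 500 and 700.

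**The case against.** The strongest reply is that the protocol nearly supplies the answer. A site that takes the next lower level from Table 5 would go from 175 to 100 and from 300 to 200, which are the rows proposed here. These tables are also recommendations, Section 6.2 lets investigators reduce outside the criteria without a deviation, and Section 6.1.2 provides for regular meetings between sponsor and investigators. This stands as a limit on the harm. It does not close the gap: 175 and 300 are not Table 5 levels, no sentence says Table 5 takes over when Table 8 ends, and Section 6.2 permits a reduction without naming a dose.

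Four stronger readings are tempting and are not supported.

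- **The tables conflict on the first reduction.** Table 5 would give 200 from 350 and 350 from 500, where Table 8 gives 175 and 300. But Section 6.2.1 names Table 8, so where a row exists it governs.
- **The cap promises three reductions from every dose.** It is a ceiling. The chains from 50 and 100 mg/d properly end sooner, at the floor.
- **175 mg/d cannot be split at all.** An unequal 100 + 75 mg split can be made. Only the equal split that footnote a requires fails.
- **The SAP shows that 300 mg/d is a treatment cohort.** SAP Section 5.6.2.2 lists "50mg cohort, 100mg cohort, 200mg cohort, 300mg cohort, 500mg cohort", but Table 5 has no 300 mg level and the entry may be a labelling error. It is not used as evidence here.

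**Conclusion.** The point holds as an incomplete dosing instruction. No dose is stated for a second reduction from 350 or 500 mg/d, or a third from 700 mg/d, although each is allowed by the cap and lies above the floor. The missing rows are close to missing detail. The BID instruction is wrong as written, because it yields 87.5 mg twice daily, but it matters only if BID is adopted, 350 mg/d is given that way, and a patient there needs a reduction.

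The effect is on patient dosing and its consistency across sites. Sample size, error rates and primary analyses do not change. The documents give no expected frequency of repeat reductions, so the number of patients affected cannot be estimated. In Parts B and C the gap arises only if a dose of 350, 500 or 700 mg/d is carried forward; the chains from 200 mg/d and below are complete.

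This rests on Table 8 governing reductions, BID doses being equal, and tablets being taken whole, all of which the protocol states. A correction is worth making because it is cheap and concerns a safety step.

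**What to change.** Keep every existing Table 8 step and make three changes.

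1. Add two rows: 175 to 100 mg/d and 300 to 200 mg/d.
2. Extend footnote a: under BID, a current dose of 350 mg/d reduces to 150 mg/d (75 mg twice daily), and the next step is 100 mg/d.
3. State that the next lower dose level in Tables 9 and 10 means the Table 8 step.

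The cost is two rows, one footnote clause and one sentence. No QD reduction already in the table changes. The downside is that the first BID cut from 350 mg/d becomes 57% instead of the 50% that cannot be dispensed. The change covers the six planned levels; an intermediate level, or one above 700 mg/d opened under Section 6.1.1, would need its own row when it is opened.
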